2.3.2.2 Prior and Concomitant Medications Date

If the start date of medication is completely missing in which the day, month, and year are all unknown or only the day is known, then the start date will not be imputed. Similar rules will be applied for the end date of medication.

- For the partial start date of medication,
 - If the year is present and the month and day are missing or the year and day are present and the month is missing, set month and day to January 1.
 - If the year and month are present and the day is missing, set day to 1st day of month.
 - If the imputed start date of medication is after the non-imputed end date of medication, then the start date will be set to the end date of medication.
- For the partial end date of medication,
 - If the year is present and the month and day are missing or the year and date are present and the month is missing, set month and day to December 31.
 - If the year and month are present and the day is missing, set day to last day of the month.

3 Disposition and Exit Status

3.1 Screening Log Data

Number of screen failures and reason for failure will be summarized.

3.2 Disposition and Exit Status

The number and percentage of subjects in each analysis population will be summarized by treatment group and overall. For the subjects who discontinued early, the primary reason for discontinuation will be summarized. Duration in DB and OL period will be calculated as below and will be summarized:

- For subjects were not re-treated, duration in DB period will be calculated as (date of discontinuation/completion – date of initiation of DB treatment + 1).
- For subjects were re-treated, duration in DB period will be calculated as (date of initiation of OL treatment – date of initiation of DB treatment + 1); duration in OL period will be calculated as (date of discontinuation/completion – date of initiation of OL treatment + 1);

Study day of discontinuation will be calculated as below and listed.

- For subjects that terminate the study early and were not re-treated, study day of discontinuation will be calculated as (date of discontinuation – date of initiation of DB treatment + 1).
- For subjects that terminate the study early and were re-treated, study day of discontinuation will be calculated as (date of discontinuation – date of initiation of OL treatment + 1).

Number and percentage of subjects randomized in each country and site will be presented by treatment group and overall.

A data listing for all subjects will display disposition characteristics, including date of initiation of the DB treatment and OL treatment if applicable, study completion status, last study day/date completed, reason(s) for non-completion, date of early termination assessment/study day of termination, and any specific comments related to non-completion.

3.3 Protocol Deviations

Protocol deviations (PDs) will be summarized by deviation type.

A data listing by treatment group, subject and time point will present details of each deviation.

4 Demographics and Other Baseline Characteristics

4.1 Demographics

Descriptive statistics for age, weight, body mass index (BMI) and height at study entry will be presented. Frequency tabulations for sex, ethnicity, age group (<65, >=65 years) and race (Caucasian, Black, Asian, American Indian or Alaskan Native, Other) and race (Caucasian and non-Caucasian) will be presented. This will be done for the ITT population by treatment group.

BMI is calculated as $BMI \text{ (kg/m}^2\text{)} = \text{weight (kg)} / \text{height}^2 \text{ (m)}$.

4.2 Baseline Disease Characteristics

4.2.1 OAB Related Baseline Characteristics Recorded on the Electronic Case Report Form (eCRF)

OAB related baseline characteristics summarized in [Table 3](#) and recorded on the electronic case report form (eCRF) from the Screening Visit will be summarized for the ITT population by treatment group.

Duration of the OAB symptoms in months is calculated as the number of months from onset date of OAB symptoms at diagnosis to the informed consent date at the screening.

$(\text{Date of Informed Consent} - \text{Overactive Bladder Onset date} + 1) / 30.25$

Table 3: Overactive Bladder Related Baseline Characteristics from eCRF

Characteristic	Summarized as	Categories
Number of urinary tract infection (UTIs) occurring over the past 6 months	Continuous	N/A
Duration of OAB symptoms (in months)	Continuous	N/A
Post-void residual (PVR) volume (mL)	Continuous	N/A
Bladder volume (mL)	Continuous	N/A

4.2.2 Baseline Characteristics from 3-day Bladder Diary

Baseline characteristics derived from the 3-day bladder diary prior to the Randomization Visit will be summarized as continuous variable for the ITT Population with following listed characteristics in [Table 4](#).

Table 4: Baseline Characteristics from 3-Day Bladder Diary

Characteristic	Corresponding Items in 3-Day Bladder Diary	Summarized as	Categories
Daily average number of incontinence episodes	Did you have accidental urinary leakage? as “Yes”	Continuous	N/A
Daily average number of urgency episodes	Was this episode associated with a sudden and urgent need to urinate? as “Yes”	Continuous	N/A
Daily average number of urgency urinary incontinence (UUI) episodes	Did you have accidental urinary leakage? as “Yes” +	Continuous	N/A
	Was this episode associated with a sudden and urgent need to urinate? as “Yes”	Categorical	≤ 9 versus > 9
Daily average number of micturitions	Did you urinate into the toilet? as “Yes”	Continuous	N/A
Daily average number of nocturia episodes	Did this episode wake you from night sleep? as “Yes”	Continuous	N/A
Total volume voided per 24 hours	Record volume collected in 24 hr for this urinary episode	Continuous	N/A

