### **6.3.4        Bladder Diary**

All patients will be provided a e-Diary in which to record electronically 3 consecutive days of required bladder diary information. Prior to receiving the e-Diary, patients will be instructed and trained on the use of the electronic diary and the data to be collected. Patients will be required to collect bladder diary data over 3 consecutive 24-hour periods during the week prior to scheduled clinic visits (for screening period only, the diary can be completed for 3 consecutive 24-hour periods at any time during the screening period). Patients must bring the e-Diary to each clinic visit. The electronic diary will capture the following information (terms used on the diary will be patient friendly):

- date and time of urinary episode
- episodes of micturition (toilet voids)
- episodes of urinary incontinence
- episodes of urgency
- episodes of nocturia (voids that awaken from normal sleep)
- start and stop date of CIC
- volume of each void measured over one 24-hour period during the 3-day bladder diary collection period. This will be used to calculate the volume voided per voiding episode (see [Section 6.3.5 Total Volume Voided](#)).

More detailed instructions on the use of the e-Diary and completion of the electronic patient bladder diary will be provided to the patient.

The electronic diary data will also be used to satisfy eligibility requirements for study entry, as well as to qualify the patient for Treatment 2.

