### **6.3.5        Total Volume Voided**

The total volume of voided urine will be measured by all patients over one 24-hour period during the 3-day bladder diary collection period. Urine collection containers needed to perform this measurement will be supplied to the patients by the sites. Patients are to

measure the volume of each void (voluntary or catheterization) as it occurs and enter that amount (with time of void) into their diary.

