5.3.4 Change from Baseline in Daily Average Number of Nocturia Episodes

Change from baseline in daily average number of nocturia episodes at Week 1, Week 2, Week 6, Week 12, Week 24, and Week 30 will be analyzed following the same algorithm as described in [Section 5.3.2](#).

[figure not shown]
5.3.5 Proportion of subjects who have a positive treatment response on the Treatment Benefit Scale (TBS)

[figure not shown]
Treatment Benefit Scale (TBS) is a single-item 4-point scale is used to assess the subject-reported benefit of treatment of OAB with respect to improvement or worsening of their condition at Week 12. Responses will be summarized descriptively by treatment groups.

- 1- greatly improved
- 2- improved
- 3- not changed
- 4- worsened

TBS responders defined as subjects who rated their perception of response to treatment as either ‘greatly improved’ or ‘improved’ at Week 12 compared to baseline. This indicator will be derived for Week 12. The analysis will follow the same algorithm as described in [Section 5.3.1](#).

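### SAP Table 4 counts any episode that wakes the patient as nocturia, while the protocol counts only voids that do so; as written, leak-only awakenings can enter the secondary endpoint

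*SAP*

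**What the plan says.** Protocol section 6.3.4 lists what the bladder diary captures. Nocturia appears as "episodes of nocturia (voids that awaken from normal sleep". Micturition is listed as "episodes of micturition (toilet voids", and urinary incontinence has its own entry. Protocol section 6.3.5, on voided volume, tells patients to "measure the volume of each void (voluntary or catheterization) as it occurs". In the protocol, then, a void is voluntary or by catheter, and leakage is a different kind of event.

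SAP section 4.2.2, Table 4, links each diary-based count to its diary item. For nocturia the only item is "Did this episode wake you from night sleep", answered Yes. The toilet item is used for micturitions, in the row directly above, and is not joined to the nocturia row. The row for urgency urinary incontinence joins two items with a plus sign.

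SAP section 5.3.4 specifies the analysis of "Change from baseline in daily average number of nocturia episodes at Week 1, Week 2, Week 6, Week 12, Week 24, and Week 30" and refers to section 5.3.2 for the method. SAP section 8 declares no departure from the protocol-specified analysis.

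**The concern.** Nocturia is one of five secondary efficacy endpoints. It is tested two-sided at 0.05 without multiplicity adjustment and reported at six visits. If the programmer codes Table 4 as it stands, an episode that wakes the patient with leakage but no void enters the nocturia count. That is not the quantity the protocol says is measured, and the SAP does not declare the difference.

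The extra events are of one kind: leakage. Treatment is expected to reduce leakage more than placebo does. If leak-only awakenings occur and fall with treatment, part of a nocturia difference could reflect fewer leaks and not fewer night-time voids. A reader of the results could not tell the two apart.

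**Working it through.** The documents state no nocturia rate, effect or standard deviation, and no rate of leak-only awakenings. There is no plan figure to reproduce, so the check compares the definitions.

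**Step 1: is Table 4 the operative definition?** It is titled as a table of baseline characteristics, so other sources were checked first.

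- SAP 5.3.4 points to 5.3.2, which gives the ANCOVA model and no episode definition.
- SAP 2.3.1.2 points to 2.3.1.1, which gives the valid-day, averaging and imputation rules and does not define a nocturia episode.
- Protocol 7.2.2 applies the primary diary algorithm to the first three secondary endpoints only, and nocturia is fourth on the list. SAP 2.3.1.2 says the first four. Neither says what counts as a nocturia episode.

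A change from baseline needs the same count at both times, and the baseline count is also the ANCOVA covariate. It is therefore a sound inference, though not stated, that the Table 4 rule carries to post-treatment visits.

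**Step 2: where do the two rules differ?** Take the episodes that involve a void or a leak:

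| Wakes patient | Void | Leak | Protocol 6.3.4 | SAP Table 4 |
|---|---|---|---|---|
| No | any | any | not counted | not counted |
| Yes | toilet | no | counted | counted |
| Yes | toilet | yes | counted | counted |
| Yes | catheter | either | counted (a void under 6.3.5) | counted |
| Yes | none | yes | **not counted** | **counted** |

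Only the last row differs.

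**Step 3: what does that do to the endpoint?** Write V for awakenings with a void and L for leak-only awakenings, both as daily averages. The protocol count is V and the SAP count is V + L. Because L is never negative, the SAP count is never the smaller of the two. The between-group difference in change from baseline becomes

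difference in change of V + difference in change of L.

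The second term is the departure from the protocol's endpoint. It is zero if L is always zero. Otherwise its size depends on data that the documents do not give.

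**Step 4: would a toilet condition alone repair it?** Not safely. Protocol 6.3.5 counts catheterization as a void. How a catheterized void is entered against the toilet item is not shown. If it is entered as No, a toilet-only condition would drop the fourth row of the table, which the protocol includes.

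**The case against.** The strongest reply is that the available text cannot show that the miscount occurs. The e-Diary screens and question flow are not shown, and the patient's detailed diary instructions lie outside the text. If the wake item appears only after a void has been entered, the two rules give identical counts. Table 4 may also be meant only to name source items: its row for total voided volume names an item without saying that values are summed. The plus sign in the urgency incontinence row shows that two items are needed there, but it does not prove that no filter applies elsewhere.

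This stands as a limit on the consequence. It does not remove the mismatch, because the derivation on paper is wider than the protocol's and nothing visible narrows it.

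A reader might go further and infer that the nocturia endpoint re-measures incontinence, so that any fall in night-time leakage shows up as a nocturia benefit. The documents do not support that. Leaks that do not wake the patient count under neither rule, and awakenings with both a leak and a toilet void count under both. Some overlap between diary endpoints would also remain after correction, since one episode can count as a micturition, an urgency episode, an incontinence episode and a nocturia episode.

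A reader might also try to size the effect by applying an assumed share to the planning difference in incontinence (2.8 − 0.95 = 1.85 episodes per day, protocol section 7.5). No share has a source in the documents, the 1.85 covers leaks over the whole 24 hours and not those at night, and a share of zero is possible.

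**Conclusion.** The point holds as a mismatch of definitions. Read literally, the SAP's nocturia count is broader than the protocol's, because awakenings with leakage and no void can be included. For those episodes only, the endpoint may overlap with incontinence.

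No numeric effect is claimed, and it could be zero. The conclusion rests on two assumptions: that Table 4's rule is also used after baseline, and that the e-Diary does not already confine the wake item to voids. Severity is minor. The primary endpoint and the sample size are unaffected.

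**What to change.** Define a nocturia episode in the SAP as one with the wake item answered Yes **and** a void in the protocol's sense, meaning the toilet item answered Yes or a catheterized void as in protocol section 6.3.5. Apply the definition at baseline and every post-treatment visit, and refer to it from SAP section 5.3.4.

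If the e-Diary already limits the wake item to voids, one sentence saying so closes the point. If the wider rule is kept on purpose, declare it in SAP section 8 and add the void-only count as a sensitivity analysis.

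The cost is one line of SAP text and one extra condition in the derivation. The wake and toilet items are already collected. The one thing to check is how the e-Diary records a catheterized void. SAP section 1 allows version-controlled revisions before database hard lock.

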4.3 Prior Medications

Prior medications are medications which started and ended before the initiation of DB treatment.

Previous medications are coded with World Health Organization – Drug Dictionary Enhanced (WHODDE), and will be summarized by chemical subgroup (ATC 4th level) and preferred World Health Organization (WHO) name by treatment group for the ITT population. Prior medications summary will include prior OAB medications, prior urinary tract infection (UTI) medication, and prior non-UTI medication.

Subjects taking the same medication multiple times will be counted once per medication.

4.4 Past Medical History

Medical history (other than for overactive bladder) and prior surgical procedure is coded in MedDRA, and will be summarized by System Organ Class (SOC) and Preferred Term (PT), by treatment group for the ITT Population.

5 Efficacy Analyses

Statistical tests for all efficacy endpoints will be 2-sided at significance level of 0.05. No adjustment for the multiplicity of the endpoints will be performed.

The efficacy variables during the open-label period, no statistical tests will be performed for summaries of efficacy variables.

5.1 Collection of Primary Efficacy Measurement(s) and Derivation of Primary Efficacy Variable(s)

The primary efficacy endpoint is:

- Change from baseline in number of episodes of urinary incontinence at Week 12 as recorded by the subject in the 3-day bladder diary.

Refer to [Section 2.3.1.1](#) for the algorithms for diary data conventions.

Change from baseline in number of episodes of urinary incontinence at Week 12 is derived as number of episodes of urinary incontinence per 24 hour at Week 12 minus number of episodes of urinary incontinence per 24 hour at Baseline.

5.2 Primary Efficacy Analyses

5.2.1 Primary Analyses of Primary Efficacy Variable(s)

[figure not shown]
Let μ_1, μ_2 be the true mean change from baseline at Week 12 in the daily average number of episodes of urinary incontinence for BOTOX 100 U and placebo, respectively.

The hypothesis of the primary analysis will be formulated as

$$H_0: \mu_1 - \mu_2 = 0 \text{ vs}$$

$$H_a: \mu_1 - \mu_2 \neq 0.$$

The primary endpoint will be analyzed using an analysis of covariance (ANCOVA) model with treatment as a factor at 2 levels, and the number of UUI episodes reported at baseline (≤ 9 versus > 9 daily episodes, during the 3-day bladder diary at baseline) and baseline daily average number of episodes of incontinence as covariates. Least squares (LS) mean for each treatment group and 95% confidence interval (CI) will be calculated.

5.3 Secondary Efficacy Analyses

5.3.1 Proportion of Subjects who Achieved 100% Reduction in Urinary Incontinence Episodes from Baseline

Subject who achieves 100% reduction in urinary incontinence episodes (complete continence) from baseline is defined as:

- If post-treatment urinary incontinence episodes = 0, set the 100% reduction in urinary incontinence episodes indicator equal to Y.
- If post-treatment urinary incontinence episodes > 0, set the 100% reduction in urinary incontinence episodes indicator equal to N.

This indicator will be derived for Week 1, Week 2, Week 6, Week 12, Week 24, and Week 30, respectively.

This endpoint will be analyzed using a Cochran Mantel-Haenszel (CMH) test adjusting for the number of UUI episodes reported at baseline (≤ 9 versus > 9 daily episodes, during the 3-day bladder diary at baseline) at each scheduled visit. Odds ratio and 95% CI (BOTOX/placebo) will be calculated.

5.3.2 Change from Baseline in Daily Average Number of Micturition Episodes

This endpoint will be analyzed at each scheduled visit (Week 1, Week 2, Week 6, Week 12, Week 24, and Week 30) using an ANCOVA model with treatment as a factor and baseline value corresponding to the given endpoint and the number of UUI episodes reported at baseline (≤ 9 versus > 9 daily episodes, during the 3-day bladder diary at baseline) as covariates. A 95% CI for the least-squares mean difference of a given endpoint between the two treatment groups will be calculated.

5.3.3 Change from Baseline in Daily Average Number of Urgency Episodes

Change from baseline in daily average number of urgency episodes at Week 1, Week 2, Week 6, Week 12, Week 24, and Week 30 will be analyzed following the same algorithm as described in [Section 5.3.2](#).

5.3.4 Change from Baseline in Daily Average Number of Nocturia Episodes

Change from baseline in daily average number of nocturia episodes at Week 1, Week 2, Week 6, Week 12, Week 24, and Week 30 will be analyzed following the same algorithm as described in [Section 5.3.2](#).

[figure not shown]
5.3.5 Proportion of subjects who have a positive treatment response on the Treatment Benefit Scale (TBS)

[figure not shown]
Treatment Benefit Scale (TBS) is a single-item 4-point scale is used to assess the subject-reported benefit of treatment of OAB with respect to improvement or worsening of their condition at Week 12. Responses will be summarized descriptively by treatment groups.

- 1- greatly improved
- 2- improved
- 3- not changed
- 4- worsened

TBS responders defined as subjects who rated their perception of response to treatment as either ‘greatly improved’ or ‘improved’ at Week 12 compared to baseline. This indicator will be derived for Week 12. The analysis will follow the same algorithm as described in [Section 5.3.1](#).

5.5.2 Analysis for Continuous Endpoints

Analysis for continuous endpoints at each visit will be conducted using the similar ANCOVA models as stated in [Section 5.3.2](#) except for change from baseline in daily UUI episodes. For change from baseline in daily UUI episodes analysis, number of UUI episodes reported at baseline (≤ 9 versus > 9 daily episodes) will be excluded from the model.

[figure not shown]
A paired t-test will be performed for the comparison between baseline and a post-treatment value at each visit for each endpoint. This analysis will follow the same algorithm as described in [Section 5.4](#).

5.5.3 Analysis of Categorical Endpoints

Analysis for categorical endpoints at each visit will be conducted using CMH test in [Section 5.3.1](#). Point estimate and 95% CI for the odds ratio will be calculated for each endpoint at each visit.

5.5.4 Analysis of Time to Request of Re-Treatment

The time-to-request of re-treatment between the two treatments will be analyzed using the log-rank test. Kaplan-Meier estimates of the time-to-request of re-treatment will be provided. A 95% CI for the median time-to-request of re-treatment for each treatment will be calculated.

6 Safety Analyses

All safety analyses will be conducted on the safety population. No inferential comparison between treatment groups will be performed for the safety analysis.

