**Treatment 2:**

A second treatment may be administered provided the patient qualifies for Treatment 2 (see below criteria) and only if the Day of Treatment Criteria are fulfilled. All patients will receive BOTOX 100 U for their second treatment. The Qualification for Treatment 2 can occur any time starting at Week 12 up to Week 30 post Treatment 1 and must occur during a clinic visit, either at a regular prescheduled visit or an additional unscheduled visit, depending on the timing of the request for a second treatment. If the patient does not request a second treatment, then the Week 30 clinic visit will be an exit visit.

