## 2.2 Clinical Hypotheses

BOTOX 100 U is more effective compared to placebo, when injected into the bladder using the alternative paradigm (2 trigonal and 8 peri-trigonal injections), in reducing the number of daily urinary incontinence episodes from baseline at Week 12.

BOTOX 100 U has an acceptable/better safety profile, including the risk of incomplete bladder emptying and need for clean intermittent catheterization (CIC), when administered as 10 injections into the lower part of the bladder (2 trigonal and 8 peri-trigonal) of patients with OAB with urinary incontinence.

BOTOX 100U administered into 10 injection sites limited to the lower portion of the bladder (alternative paradigm) rather than 20 sites in the posterior wall is effective in achieving efficacy in patients with OAB while reducing the risk of incomplete bladder emptying in those patients.

BOTOX 100 U, administered using an alternative injection paradigm, is effective for longer duration than placebo as assessed by the difference between treatment groups in the time to qualification for second treatment (qualification for Treatment 2 criteria provided in [Section 5.10.1](#) Request/Qualification for Treatment 2) during the 30 weeks of follow-up after the first treatment injection.

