## **5.10        Retreatment**

### **5.10.1      Request/Qualification for Treatment 2**

Patients may request Treatment 2 at the Week 12 clinic visit or any time thereafter up to Week 30. A qualification visit will be added to the patient's schedule if the request for retreatment is made outside the regular prescheduled visits. A clinic visit (prescheduled or unscheduled) at which the patient is assessed after making a request for a second treatment will then become a Qualification for Treatment 2 visit, and is no longer considered the post-treatment visit, and the appropriate eCRFs should be completed. Treatment 2 should occur within 28 days of qualification and no later than Week 34 (+/-7 days). The patient must meet all qualification criteria before Treatment 2 can occur.

The 'Qualification for Treatment 2 Criteria' are:

- Patient must initiate request for Treatment 2
- Patient experiences  $\geq 2$  episodes of urinary urgency incontinence, with no more than 1 urgency incontinence-free day, as determined by the 3 consecutive days of bladder diary completion in the week prior to the qualification for Treatment 2 visit (ie, Week 12, 24 or 30 post Treatment 1 or an additional visit, depending on the timing of the retreatment request).
- PVR urine volume must be  $< 200$  mL.
- Investigator deems that Treatment 2 is medically appropriate and no condition or situation exists which, in the investigator's opinion, puts the patient at significant risk from receiving a second treatment.
- A minimum of 12 weeks must have elapsed since Treatment 1.

Once a patient has met the 'Qualification for Treatment 2 Criteria', the patient is considered qualified for Treatment 2 and may proceed with the treatment visit (see [Section 5.10.2](#)). The Treatment 2 visit may occur on the same day of qualification or may be scheduled on another day if the Treatment 2 criteria are not met. If the Treatment 2 visit is rescheduled, visit procedures for which the patient has already been qualified do not need to be repeated.

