### 7.3.2 Secondary Efficacy Analyses

The 5 secondary endpoints are listed in [Section 7.2.2](#).

The analysis of all secondary endpoints will be based on the mITT Population.

The first and the last secondary endpoints on the list are categorical variables, and they will be analyzed using a Cochran Mantel-Haenszel (CMH) test with the number of UUI episodes reported at baseline ( $\leq 9$  versus  $> 9$  daily episodes, during the 3-day bladder diary at baseline) as another categorical factor at each scheduled visit. Point estimate and the 95% CI for the odds ratio (BOTOX 100 U/placebo) will be calculated.

The second to the fourth secondary endpoints on the list are continuous variables. Each of the 3 continuous endpoints will be analyzed at each scheduled visit using an ANCOVA model with treatment as a factor and baseline value corresponding to the given endpoint and the number of UUI episodes reported at baseline ( $\leq 9$  versus  $> 9$  daily episodes, during the 3-day bladder diary at baseline) as covariates. A 95% CI for the LS mean difference of a given endpoint between the 2 treatments will be calculated. A paired t-test will be performed to compare the baseline value to a post-treatment value at each visit for each endpoint.

between the 2 treatments will be constructed. A paired t-test will be performed for the comparison between baseline and a post-treatment value at each visit for each endpoint.

The categorical endpoints will be analyzed using a CMH test with the number of UUI episodes reported at baseline ( $\leq 9$  versus  $> 9$  daily episodes, during the 3-day bladder diary at baseline) as another categorical factor at each visit. Point estimate and 95% CI for the odds ratio will be calculated for each endpoint at each visit.

The time-to-first-event endpoint will be analyzed using the Kaplan-Meier procedure for median time-to-request of re-treatment event by days (and weeks). Between-group comparisons of the 2 treatments will be performed using the log-rank test. A 95% CI for the median time-to-request of re-treatment for each treatment will be calculated.

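### Time to request of re-treatment is tested, but the visible text names no between-arm effect estimate, and the per-arm medians may not be estimable in a Week 12 to 30 window

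*SAP*

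**What the plan says.** Duration of treatment effect is a secondary objective (Protocol 2.1, SAP 1.1.3). Protocol 2.2 includes the hypothesis that BOTOX lasts longer than placebo, "as assessed by the difference between treatment groups in the time to qualification for second treatment" during the 30 weeks after the first injection.

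The visible analysis is in SAP 5.5.4: "The time-to-request of re-treatment between the two treatments will be analyzed using the log-rank test". It adds: "Kaplan-Meier estimates of the time-to-request of re-treatment will be provided", and "A 95% CI for the median time-to-request of re-treatment for each treatment will be calculated". The time-to-event text that follows Protocol 7.3.2 agrees: "Between-group comparisons of the 2 treatments will be performed using the log-rank test", with Kaplan-Meier medians and their CIs. Neither place names a stratum, a covariate or a between-arm effect measure.

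The window is set in Protocol 5.10.1: "Patients may request Treatment 2 at the Week 12 clinic visit or any time thereafter up to Week 30". The Protocol Summary closes it: "If the patient does not request a second treatment, then the Week 30 clinic visit will be an exit visit".

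For comparison:
- Protocol 7.3.1 gives a 95% CI for the difference in mean change.
- SAP 5.3.2 gives an LS mean difference with CI.
- SAP 5.3.1 and 5.5.3 give an odds ratio with CI.

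All of these adjust for baseline UUI (≤ 9 versus > 9). SAP 5.5.2 states the one visible exception, the analysis of UUI itself.

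**The concern.** A log-rank test gives a p-value and no size of effect. The numerical summaries visibly planned beside it are per-arm: Kaplan-Meier estimates and medians. Medians are fragile in this window. If half the placebo arm requests at Week 12, the placebo median sits at the earliest possible time. The BOTOX median does not exist unless half that arm requests by Week 30. The longer BOTOX works, the fewer requests there are and the less the planned median can show.

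The trial could therefore report that BOTOX lasts longer than placebo without estimating by how much. The test also leaves out a baseline factor that the ANCOVA and CMH analyses use, which costs precision if that factor predicts requests. Finally, the hypothesis concerns qualification and the analysis concerns request, so it is unclear which event the result describes.

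**Working it through.** **1. The plan's own figure.** Protocol 7.5 sizes the trial on the primary endpoint only: changes of -2.8 (SD 3.45) and -0.95 (SD 2.9), 68 v 34 patients, 80% power.

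- SE = √(3.45²/68 + 2.9²/34) = 0.650
- Power = Φ(1.85/0.650 − 1.96) = Φ(0.887) = 81%, consistent with the stated 80%
- 102/0.9 = 113.3, so 114 randomised, which at 2:1 is 76 v 38

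No request rate, event count, hazard ratio or power is given for time to request. The rates and effects below are assumptions.

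**2. When the BOTOX median and its upper limit exist (n = 76, no dropout).** Let k be the number of requests by Week 30 and S = 1 − k/76.

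- The median exists if S ≤ 0.5, so k ≥ 38 (50%).
- The upper 95% limit of the median exists if the upper limit for S at Week 30 is at most 0.5. On the log-log scale that limit is exp{−exp[ln(−ln S) − 1.96·s]}, with s = √(k/(76(76 − k)))/|ln S|. It is 0.502 at k = 46 and 0.489 at k = 47, so k ≥ 47 (62%). The linear form gives the same cut-off.

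With X ~ Binomial(76, p):

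| BOTOX request rate p | Median not reached, P(X ≤ 37) | Upper limit not reached, P(X ≤ 46) |
|---|---|---|
| 40% | 95% | 100% |
| 50% | 45% | 97.5% |
| 55% | 16% | 86% |
| 60% | 3% | 58% |
| 65% | 0.3% | 24% |
| 70% | < 0.1% | 5% |
| 80% | 0 | 0 |

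Simulation with 10% dropout is similar: 48% / 97% at 50%, 4% / 58% at 60%, < 0.1% / 5% at 70%.

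**3. What stays estimable.** The request-free proportion at Week 30 exists at any of these rates. At S = 0.5 its 95% half-width is 1.96·√(0.5 × 0.5/76) = 0.11. If 50% of BOTOX and 25% of placebo patients are request-free, the half-width for the difference is 1.96·√(0.25/76 + 0.1875/38) = 0.18.

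**4. Power with and without adjustment.** Simulation at 76 v 38 with 10% dropout, two-sided 5%, and requests that would have come earlier placed at Week 12. There were 800 replicates per case (Monte Carlo error about ±3 points; comparisons within a case are paired). Entries are unadjusted log-rank → Cox with one continuous baseline severity covariate.

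| Requests by Week 30, BOTOX / placebo | Not prognostic | HR 1.35 per SD | HR 1.8 per SD |
|---|---|---|---|
| 40% / 65% | 74.4 → 73.5 | 71.1 → 73.4 | 74.4 → 80.5 |
| 50% / 75% | 77.5 → 77.1 | 77.9 → 79.6 | 75.5 → 86.1 |
| 60% / 80% | 63.6 → 63.4 | 63.1 → 66.7 | 63.5 → 75.4 |
| 60% / 85% | 85.1 → 83.9 | 87.7 → 90.9 | 87.0 → 94.4 |
| 70% / 90% | 80.1 → 79.4 | 82.3 → 85.0 | 79.0 → 90.7 |

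The gain is nil if severity is not prognostic, about 2 to 4 points if moderately so, and about 6 to 12 if strongly so. Simulated type I error of the log-rank test was 4.1%.

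Holding requests until Week 12, compared with free timing up to Week 30, cost the log-rank test about 1 to 2.5 points with no or moderate prognostic effect, and 2 to 7 with a strong one.

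**5. Request against qualification.** Under Protocol 5.10.1 a request is one of several qualification criteria, beside the diary, residual-volume and investigator criteria. Protocol 5.6.1 records the reasons for a request whether or not the patient qualifies. The two events can therefore differ. Since qualification requires a request, its rate cannot exceed the request rate, so medians for time to qualification would be no easier to reach.

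**The case against.** A reader might infer that the Week 12 to 30 window makes the BOTOX median usually inestimable and so costs power. Neither part is supported. With no request rate in the documents, how often the median fails is unknown: at a 70% rate it is almost always reached. The log-rank test does not use the median, and a period without events in either arm costs it nothing in itself. The small cost comes from requests piling up at Week 12.

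A reader might also infer that the plan offers nothing beyond a p-value and two medians. That overlooks the Kaplan-Meier estimates, which can be read at any week. What they do not supply is a specified between-arm contrast with a CI.

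The argument for adjustment rests on inference. The continuing-incontinence criterion governs qualification, not request, and the documents do not say whether baseline severity predicts a request. The simulated gains are for one continuous covariate, whereas the model proposed below has two overlapping severity terms, so they are indicative only.

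Parts of Protocol 7.3 and SAP 5.4 to 5.5 are not visible. A definition, censoring rule or further analysis may stand there. An unstratified log-rank test is standard, the endpoint is outside the five listed secondary endpoints, and the trial was not sized on it. All of this stands and limits the point's weight. None of it supplies the missing estimate in the visible text.

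**Conclusion.** The point holds as a minor reporting and precision matter. In the visible text, time to request has a valid unadjusted test and per-arm summaries, but no between-arm estimate, unlike the ANCOVA and CMH analyses.

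Whether the medians fill the gap depends on an unstated request rate. For 76 BOTOX patients, the median is doubtful at about 50% requesting or fewer, and its upper limit is more likely than not to be missing at about 60% or fewer. At 70% or more both are usually available. The possible power gain from adjustment runs from none to about 12 points and rests on assumed prognostic effects. It does not make the planned test wrong.

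The mismatch between qualification in Protocol 2.2 and request in SAP 5.5.4 is visible on the page and needs no assumption.

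**What to change.** In SAP 5.5.4, keep the log-rank test, Kaplan-Meier curves and medians, and add:

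1. A Cox model (Efron ties) with treatment and the baseline covariates of the primary model: baseline daily average incontinence episodes and the UUI factor. Report the hazard ratio with 95% CI.
2. Kaplan-Meier request-free proportions just after Week 12 and at Weeks 24 and 30, with the between-arm difference and 95% CI.
3. A statement of whether the duration endpoint is time to request or time to qualification, with Protocol 2.2 and SAP 5.5.4 brought into line.

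The cost is one SAP paragraph and one table, with no new data. The drawback is that the summary hazard ratio relies on proportional hazards; the fixed-week proportions do not.
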